13.2 Schedule of Procedures

Study Phase	Screening/Pre-Intervention	Intervention				3-Month Follow-Up
Visit Number	1	2	3	4	5	6
Informed Consent	X					
Review Eligibility	X					
Interview	X					
Surveys	X	X	X	X	X	X

PROTOCOL TITLE: Behavior, Biology, and Well-Being (BeWell) Study

HMP or active control (Intervention and active control groups)		X	X	X	X	X
Video recording task	X	X	X	X	X	X
Pattern Separation Task	X				X	X
Microbiome Sample	X					X
Blood Spot Sample	X					X
Adverse Event Assessment					X	X

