- ““(1) Is intended as an implant and presents a potential for serious risk to the health, safety, or welfare of a subject;
- (2) Is purported or represented to be for a use in supporting or sustaining human life and presents a potential for serious risk to the health, safety, or welfare of a subject;
- (3) Is for a use of substantial importance in diagnosing, curing, mitigating, or treating disease, or otherwise preventing impairment of human health and presents a potential for serious risk to the health, safety, or welfare of a subject; or
- (4) Otherwise presents a potential for serious risk to the health, safety, or welfare of a subject””

The Healthy Minds Program (HMP) in this study is a smartphone app that includes both didactic content and guided meditation practices. The device will be used to aid development of well-being by training skills that are based on scientific studies (the didactic content). It also includes guided meditation practices found in widely available evidence-based treatments such as mindfulness-based stress reduction, mindfulness-based cognitive therapy, cognitive behavioral therapy, acceptance and commitment therapy, and other widely used smartphone meditation apps such as Headspace and Calm.

The use of the device in this study does not meet the definition of a significant risk device as it is not an implant, is not used to sustain human life and poses no serious risk to health, safety or

PROTOCOL TITLE: Behavior, Biology, and Well-Being (BeWell) Study

welfare of a subject. The device may mitigate symptoms of depression, anxiety and stress, but has not shown to pose a serious risk to health, safety, or welfare.

Summary of prior uses: HMP has been tested by our group in two randomized controlled trials (ns = 343, 662; Goldberg et al., 2020; Hirshberg et al., 2021). In both trials, HMP was shown to produce larger reductions in psychological distress (composite of depression, anxiety, and stress) relative to a waitlist control condition. Participants in both studies were drawn from the general population, although ~75% in each sample reported elevated depression and/or anxiety symptoms at baseline. Effects were similar when restricted to those in the clinical range at baseline. No serious adverse effects were reported in either study. In support of HMP's safety, HMP was shown to produce lower rates of clinically significant increases in symptoms relative to a waitlist condition.

References:

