5. Weeks 1 to 3 Assessments (Timepoints 2, 3, 4). Participants will complete a small subset of the surveys in REDCap as well as the video task at the end of weeks 1, 2, and 3. It will take

PROTOCOL TITLE: Behavior, Biology, and Well-Being (BeWell) Study

approximately 30 minutes to complete these measures. Participants will be given one week to complete each weekly assessment.

6. Week 4/Post-Intervention Assessment (Timepoint 5). Participants will complete the same surveys and games (behavioral task and video task) in REDCap as was done for the pre-intervention assessment; the invite for these measures will be sent at the end of week 4. It will take approximately 60-90 minutes to complete these measures. Participants will be given 2 weeks to complete this assessment. Participants in the intervention or active control groups will have the option to continue using the HMP after this timepoint. We will continue to monitor app data throughout the study to learn more about its long-term impact on well-being.
7. 3-Month Follow-Up Assessment (Timepoint 6). Participants will complete the same surveys and games (behavioral task and video task) in REDCap as was done for the pre-intervention and post-intervention assessments; the invite for these measures will be sent 90 days after the date of the post-intervention invite. It will take approximately 60-90 minutes to complete these measures. Participants will be given 2 weeks to complete this assessment. Another microbiome kit and blood spot collection kit will be mailed to participants to collect samples; they will have 1 month to collect.

Healthy control participants will complete only #1 to #3.

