Decentering subscale of the Experiencing Questionnaire	11			X	X	X	X
DUDIT	11	X					
Five Facet Mindfulness Questionnaire (FFMQ) – Awareness and Non-Judgment Subscales	8			X	X	X	X
Flourishing Measure	12			X	X	X	X
General Anxiety Disorder (GAD-7)	7			X	X	X	X
General Availability	1			X			
Growth Mindset Scale for Well-Being	3			X		X	X
Healthy Minds Index (HMI)	17			X		X	X
Inclusion of Nature in Self	1			X		X	X
Lasting Effects Questionnaire	2						X
Life Orientation Test Revised (LOT-R)	10			X		X	X
Marlowe-Crowne Social Desirability Scale (MCSD)	13			X			
Medication Questionnaires (Health History, Current Health and Medication use, and biospecimen collection questions)	Varies			X		X	X
Meditation and App Usage Questionnaire	5			X		X	

PROTOCOL TITLE: Behavior, Biology, and Well-Being (BeWell) Study

Mindfulness Adherence Questionnaire informal practice items only -- app groups only	12				X	X	X
Mindfulness-Based Program Meditation-Related Adverse Effects Scale (MBP-MRAES) – app groups only	15					X	
NIH Toolbox Loneliness	5			X	X	X	X
NIH Toolbox Meaning and Purpose	18			X	X	X	X
Patient Health Questionnaire -- depression scale (PHQ-8)	8		X	X	X	X	X
Patient Health Questionnaire – depression scale (PHQ-9)	9	X					
Patient-Reported Outcome Measurement Information System (PROMIS) Computer Adaptive Version for Sleep Disturbances	Varies			X	X	X	X
Perceived Stress Scale (PSS)	10			X		X	X
Perseverative Thinking Questionnaire (PTQ)	15			X		X	X
Post-pattern separation question	1			X		X	X
Post-video task question	1			X	X	X	X
Pre and Post Practice Questions	3				X	X	
Problematic and Risky Internet Use Screening Scale (PRIUSS)	3			X		X	X

PROTOCOL TITLE: Behavior, Biology, and Well-Being (BeWell) Study

PROMIS pain inference measure	40			X		X	X
PROMIS pain intensity measure	1			X		X	X
Satisfaction With Life Scale	5			X		X	X
Subjective Happiness Scale	4			X		X	X
Treatment Expectancies – app groups only	6					X	
SCID-5-RV	Varies		X				
Video Recording Measures	N/A			X	X	X	X
Pattern Separation (Mnemonic Similarity Task)	N/A			X		X	X
Dried Blood Spot Collection	N/A			X			X
Microbiome Collection	N/A			X			X
Environmental Toxin Questionnaire	6			X			

3. Behavioral Measures. Participants will receive the link for the behavioral tasks in REDCap. The behavioral task completion will take approximately 10 minutes.

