23.0 Provisions to Monitor the Data to Ensure the Safety of Participants

23.1

Adverse events will be tracked (including details of the incident, actions taken, and follow-up steps) by study staff and reported to the PI. The PI will be responsible for the monitoring and reporting of adverse events as necessary to the UW IRB.

Other notable incidents that occur during recruitment, consent, study assessments, but are determined to be unexpected and related to the study procedures, will be reported in a detailed log on an annual basis (at the time of continuing review). The PI will be responsible for informing the IRB immediately of any life-threatening incidents as well as take appropriate action to stop the study, release a participant from the study, or modify procedures to reduce and/or eliminate the occurrence of the risks mentioned above.

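### The visit schedule marks an adverse event assessment at visits 5 and 6, but the only named adverse-effects scale is given once, at post-intervention, to the app groups, and no between-arm harms comparison is planned

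*Combined protocol and SAP*

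**What the plan says.** - **Section 13.2, visit schedule.** The row "Adverse Event Assessment" is marked at visits 5 (post-intervention) and 6 (3-month follow-up). It carries no group label. The row for app use does carry one: "HMP or active control (Intervention and active control groups", marked at visits 2 to 6.
- **Section 13.3, measures table.** The only instrument named for adverse effects is "Mindfulness-Based Program Meditation-Related Adverse Effects Scale (MBP-MRAES) – app groups only", with 15 items and a single mark under post-intervention. Its 3-month cell is blank.
- **Section 13.1, step 7.** The follow-up surveys are described as the same "as was done for the pre-intervention and post-intervention assessments".
- **Section 13.1, step 6.** After the post-intervention assessment both app groups "will have the option to continue using the HMP after this timepoint". Section 13.5 adds that app data are collected until the follow-up.
- **Section 23.1.** "Adverse events will be tracked (including details of the incident, actions taken, and follow-up steps) by study staff and reported to the PI". No arm or time limit is given, and no way of asking participants.
- **Section 13.3, symptom scales.** The row "Patient Health Questionnaire -- depression scale (PHQ-8") is marked at interview, pre-intervention, the weekly timepoints, post-intervention and follow-up. GAD-7 is marked at the same points except interview. Neither row is limited by arm.
- **Sections 3.4 and 20.** Safety endpoints are entered as not applicable. The analysis section plans no interim safety analysis and describes no harms analysis at the end of the trial.
- **Section 11.1, letter on device risk.** As support for safety it reports that "HMP was shown to produce lower rates of clinically significant increases in symptoms relative to a waitlist condition".

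**The concern.** Someone running the trial from section 13.2 would expect an adverse event assessment at follow-up. Someone building the surveys from section 13.3 would program no adverse-effects scale there. The second reading decides what is collected, so the trial as tabulated would end with one solicited measurement of adverse effects, at week 4, in two of three arms.

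This matters because app use can continue after week 4. Effects that appear or persist in the following three months would reach the study team only if a participant reported them unprompted or if staff noticed them. In a fully remote trial, such reports depend on who chooses to make contact, and that may differ between arms.

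The trial will also hold the data for a between-arm comparison of symptom worsening, the type of comparison that the device letter cites from earlier trials. No such analysis is planned. If one is done later, its threshold and timepoint would be chosen with the results in view.

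**Working it through.** The plan states no figure on this point that could be reproduced. The check sets the two schedules side by side and sizes the gap.

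**1. Align the rows with their column headings.**

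| Source | Weekly | Post-intervention (visit 5) | 3 months (visit 6) | Group label |
|---|---|---|---|---|
| 13.2, adverse event row | blank | X | X | none |
| 13.3, MBP-MRAES | blank | X | blank | app groups |
| 13.3, PHQ-8 | X | X | X | none |
| 13.3, GAD-7 | X | X | X | none |

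The MBP-MRAES row keeps its empty cells in the extracted text, so the blank at three months is not a reading artefact.

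**2. Count what the scale covers under each reading of the adverse event row.**

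- If the row covers all three randomized arms: 3 arms × 2 visits = 6 cells. The MBP-MRAES fills 2 (two app arms at visit 5) and leaves 6 − 2 = 4 empty.
- If the row covers only the app groups: 2 arms × 2 visits = 4 cells. The scale fills 2 and leaves 4 − 2 = 2 empty, both at visit 6.

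Either way, visit 6 has no named instrument. The documents do not settle which reading is meant.

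**3. Time after the only administration.** The app is downloaded immediately after randomization (section 11.1). The post-intervention invite goes out at the end of week 4, and the follow-up invite 90 days after it (section 13.1).

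- Days to the post-intervention invite: 4 × 7 = 28.
- Days to the follow-up invite: 28 + 90 = 118.
- Share after the only administration: 90/118 = 0.763, or 76%.

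Both assessments have a two-week completion window. If the post-intervention survey is completed 14 days late and the follow-up on time, the share is (118 − 42)/118 = 64%. If the post-intervention survey is on time and the follow-up 14 days late, it is (90 + 14)/(118 + 14) = 104/132 = 79%.

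**4. People concerned.** Section 20.2 assigns 1,500 participants in fifths.

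- App groups: 1,500 × 4/5 = 1,200, with no scale at visit 6.
- Usual care: 1,500 × 1/5 = 300, with no adverse-effects scale at either visit.
- With the 20–50% attrition in section 4.2, assumed equal across arms, about 1,200 × 0.5 = 600 to 1,200 × 0.8 = 960 app participants would be available to answer the scale at follow-up.

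**5. Other sources of harm data.** Section 23.1 tracking is unrestricted but has no elicitation method, schedule or comparison. The Lasting Effects Questionnaire (2 items, follow-up only) is not described, so it cannot be counted as an adverse event measure. PHQ-8 and GAD-7 can show worsening in all three arms at both visits, but no analysis of worsening is specified.

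**The case against.** The strongest reply is that this is loose drafting and not a contradiction. In section 13.2 the surveys and the adverse event assessment are separate rows, and the MBP-MRAES is listed among the surveys. A staff-led assessment under section 23.1 at visits 5 and 6 could coexist with a scale given once. The sentence in section 13.1 on repeating the surveys is also only a summary: the measures table has other items that appear at one of the three main assessments and not the others, such as Treatment Expectancies. This stands in part. The documents do not prove that the adverse event row means the MBP-MRAES. But if it means something else, nothing says what is asked, by whom or of whom.

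Three stronger readings are tempting, and the documents do not support them.

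- *A reader might infer that the assessment is promised to every arm*, because the row has no group label. The surveys row has none either, yet it includes scales restricted to the app groups. A missing label therefore does not show that all arms are meant.
- *A reader might infer that harms after week 4, or relative to usual care, cannot be assessed at all.* Section 23.1 tracking and the PHQ-8 and GAD-7 schedule rule that out.
- *A reader might infer that the device-risk request depends on the worsening comparison.* The letter argues first from the regulatory definition, and it also reports no serious adverse effects in the earlier trials. The comparison is offered as added support.

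It is also fair to say that a scale of meditation-related effects need not suit usual care, and that leaving out safety endpoints fits a trial described as minimal risk. The first is why the fix does not extend the scale to that arm. The second does not explain why an assessment is scheduled at visit 6 with nothing named to carry it out.

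**Conclusion.** The point holds as a gap in specification and in data collection. As tabulated, the trial has no structured adverse-effects instrument at visit 6 in any arm and none in usual care at either visit. About 76% of the time from randomization to the follow-up invite (64–79% across the completion windows) comes after the only administration, while up to 1,200 app participants may continue using the app. No elicitation method, schedule for the general tracking or between-arm harms comparison is given.

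The 76% assumes that the scale is completed when invited and counts days from randomization. It measures time without a later administration of the scale, not time without any harm data. The documents give no expected rate of symptom worsening and no threshold for it, so the precision of a between-arm comparison cannot be stated from them.

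The primary efficacy analysis is unaffected. The change is worth making because it alters what harm data are collected and reported, at little cost.

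**What to change.** 1. **Reconcile sections 13.1 (step 7), 13.2, 13.3 and 23.1.** State which arms the adverse event row covers, which instrument or question is used at each visit, and how the tracking in section 23.1 obtains its reports.
2. **Give the MBP-MRAES to the two app groups at the 3-month follow-up as well.** That survey already carries other scales for those groups only (the Digital Working Alliance Inventory and the Mindfulness Adherence Questionnaire), so the routing exists.
3. **Pre-specify a descriptive comparison across the three arms** of the share with PHQ-8 worsening from baseline at visits 5 and 6, as differences with 95% confidence intervals. Write the worsening threshold into the plan before the data are analysed, because the documents do not give the definition used in the earlier trials. State which PHQ-8 is the baseline, since it is scheduled at both the pre-intervention assessment and the interview, and how missing scores are handled.

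The cost is 15 more items in one survey for the app groups, corrected tables and a short addition to section 20. No new visit is needed, and the PHQ-8 data are already scheduled. The downside is a slightly longer follow-up survey.

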4.0 Number of Participants

4.1

This study will enroll 1,500 participants at UW-Madison. There will also be a pilot of up to 15 participants. We will recruit approximately 250 healthy control participants who will complete baseline measures only.

4.2

The expectation is that we will have 20-50% attrition resulting in roughly 750-1200 participants completing the study.

4.3

Participants will be considered enrolled after randomization. Participants who leave the study early will not be replaced. Healthy control participants will only complete baseline measures.

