15.0 Withdrawal of Participants

15.1

We anticipate that we will withdraw a participant from the study: 1) if we determine that participation in the study is exposing the participant to an unacceptable level of risk, 2) to maintain data integrity (e.g., if a participant is not following study procedures or may be deliberately providing false information), or 3) if the study is stopped by the sponsor or researchers.

PROTOCOL TITLE: Behavior, Biology, and Well-Being (BeWell) Study

15.2

When withdrawing a participant, we will: 1) thank the participant for their participation, 2) explain the reason(s) for termination, 3) explain that the participant will be paid for the portion of the study that they completed (as described in the consent form), 4) ask the participant if they have any questions or comments about the study, and 5) inform the participant that the HMP app is available to use free of charge. We will change the participant status to withdrawn in REDCap; however, we will retain and use data collected prior to withdrawal.

15.3

When a participant chooses to withdraw from the research, we will: 1) thank the participant for their participation, 2) determine if the participant will be fully or partially withdrawing (if partial, determine which procedures the participant will be completing), 3) explain that the participant will be paid for the portion of the study that they completed (as described in the consent form), 4) ask the participant their reason for withdrawing (if they choose to provide it), 5) ask the participant if they have any questions or comments about the study, and 6) inform the participant that the HMP app is available to use free of charge. We will remove the withdrawn participant from REDCap; however, we will retain and use data collected prior to withdrawal.

15. 4

Participants who withdraw or do not complete baseline may be asked why they did not continue with participation.

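### Adverse effects are first asked about at visit 5 and never at exit, so any reported rate will describe only participants who answer at visit 5 or 6

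*Combined protocol and SAP*

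**What the plan says.** - **Schedule (13.2).** The row "Adverse Event Assessment" is marked at visits 5 and 6 and is blank at visits 1 to 4. Surveys are marked at every visit.
- **Measures table (13.3).** The entry "Mindfulness-Based Program Meditation-Related Adverse Effects Scale (MBP-MRAES) – app groups only" has a single mark, in the post-intervention column. No scale named for adverse effects appears in the weekly column. PHQ-8 and GAD-7 do appear there.
- **Timing (13.1, step 6).** For visit 5, "the invite for these measures will be sent at the end of week 4", and participants have two weeks to respond.
- **Withdrawal (15.0).** Staff may withdraw someone "if we determine that participation in the study is exposing the participant to an unacceptable level of risk". The staff-initiated close-out in 15.2 has five steps and the self-withdrawal close-out in 15.3 has six. Neither asks about adverse effects. Section 15.3 asks for a reason for leaving, which the participant may decline to give, and 15.4 says leavers may be asked why they stopped.
- **Monitoring (23.1).** "Adverse events will be tracked (including details of the incident, actions taken, and follow-up steps) by study staff and reported to the PI". No visit limit and no method of eliciting events is given.
- **Attrition (4.2).** The plan expects "20-50% attrition resulting in roughly 750-1200 participants completing the study".
- **Safety endpoints (3.4).** Not applicable. Section 20.5 plans no interim safety analysis.

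**The concern.** People who leave early because the program upset them are among those a harm measure most needs to reach, and in this schedule the first solicited question comes after they have gone. PHQ-8 is different: it is collected weekly, so an early leaver who answered one weekly survey still contributes to the mixed model in 20.4. For solicited adverse effects such a person has no observation, and no model can use data that were never collected.

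With safety endpoints set aside and no interim safety analysis, the solicited assessment is the main systematic evidence on harm that the trial will produce. A rate taken only from those still responding at the end of week 4 or later could understate harm, and early detection during the four weeks would depend on unsolicited reports in a fully remote study.

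**Working it through.** **1. The plan's own figure.** From 1,500 randomized (4.1), 20% attrition leaves 1,500 × 0.80 = 1,200 and 50% leaves 1,500 × 0.50 = 750. This matches the 750-1,200 in 4.2.

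**2. App participants who could be unscored.** Section 20.2 assigns two fifths to HMP and two fifths to active control: 600 + 600 = 1,200. If attrition is equal across arms, 1,200 × 0.20 = 240 and 1,200 × 0.50 = 600. These are upper limits on those lost before visit 5, because the 20-50% also counts people who answer visit 5 and are lost in the 90 days before the follow-up invite. The share lost before visit 5 is not stated. If it were 10% (an assumption), 1,200 × 0.10 = 120 would be unscored.

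**3. Who has no solicited observation.**

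| Participant | Opportunity to answer an adverse-effect question |
|---|---|
| Stops using the app, stays in the study | Visits 5 and 6 |
| Skips weekly surveys, returns later | Visit 5 or 6 |
| Withdraws partially (15.3) | Visit 5 or 6, if retained for those procedures |
| Answers visit 5, lost before visit 6 | Visit 5 |
| Fully withdraws, or is withdrawn, before visit 5 | None |
| Silent from before visit 5 onward | None |

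**4. Effect on a reported rate.** Let *r* be the rate among those scored, *a* the share unscored, and *k* the ratio of the unscored group's rate to *r*. The true rate is *r* × [(1 − *a*) + *a* × *k*], so reported ÷ true = 1 / [(1 − *a*) + *a* × *k*]. For *a* = 0.2 and *k* = 2 this is 1 / 1.2 = 0.833, or 17% too low. All values of *k* are assumptions.

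| *a* | *k* = 0.5 | *k* = 2 | *k* = 3 |
|---|---|---|---|
| 0.1 | 5% too high | 9% too low | 17% too low |
| 0.2 | 11% too high | 17% too low | 29% too low |
| 0.5 | 33% too high | 33% too low | 50% too low |

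The *a* = 0.5 row applies only if all of the plan's worst-case attrition falls before visit 5.

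**5. Bounds that need no value of *k*.** The true rate lies between *r*(1 − *a*) and *r*(1 − *a*) + *a*. For an assumed *r* of 10%, that is 9-19% with 10% unscored, 8-28% with 20% and 5-55% with 50%.

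**6. The two tables compared.** The schedule marks an adverse event assessment at visit 6, but the measures table shows the MBP-MRAES at post-intervention only. The schedule row is not restricted to the app groups; the scale is. The documents do not say what is asked at visit 6, or what usual care is asked at either visit.

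**The case against.** Several stronger readings are tempting, and the documents do not support them.

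- **That every dropout goes unscored.** As step 3 shows, people who only stop using the app, skip weekly surveys or withdraw partially can still answer.
- **That the rate covers only completers, with 20-50% missing.** Someone who answers visit 5 and misses visit 6 is scored but is not a completer, and the attrition figure runs to study end.
- **That the rate must be biased low.** This needs *k* above 1. Early leavers have had less exposure to the program and could report fewer adverse effects. No document gives *k*.
- **That people withdrawn for risk leave no trace.** Staff know about them by definition, and 23.1 tracking has no visit limit. What they lack is an answer to a solicited question.
- **That a planned HMP-versus-active-control harm comparison is biased.** The plan defines no harm rate, denominator or contrast. The issue concerns whatever rate is later reported.

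It is also fair to say that other harm information exists. Weekly PHQ-8 and GAD-7 would show symptom worsening, which the device-risk letter in 11.1 itself cites from earlier trials as support for safety, and 15.3 and 15.4 may yield reasons for leaving. These sources reduce the gap but do not close it. Symptom scores do not ask about effects of the program, reasons for leaving are optional, and someone who goes silent prompts no report to staff. The mixed model cannot supply the missing answers, and the missing-not-at-random analysis in 20.6 is discretionary.

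**Conclusion.** The point holds in limited form. Participants who fully leave or stop responding before visit 5 have no solicited adverse-effect observation, and a reported rate will describe visit 5 or 6 respondents. The size cannot be fixed from the documents. At most 240-600 of 1,200 app participants are affected, assuming equal attrition across arms, and the true number is smaller to the extent that losses occur after visit 5. The error in the rate could run either way; with 10-20% unscored and twice the respondents' rate among leavers, the reported rate would be 9-17% too low. Both the share and the ratio are assumptions. The change is worth making because it improves harm ascertainment at little cost.

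**What to change.** 1. Add one brief adverse-effect item to the existing week 1-3 surveys, worded identically in all arms so that usual care can answer it.
2. Add the same item to the exit contacts in 15.2 and 15.3, and offer the MBP-MRAES at exit to the app groups.
3. State the denominator: randomized participants with at least one post-randomization adverse-effect answer. Report the number never assessed by arm, with the bounds in step 5 of the working.
4. Reconcile the visit 6 mark in 13.2 with the post-intervention-only MBP-MRAES in 13.3, and state what usual care is asked.

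The cost is one item in three REDCap surveys that already take about 30 minutes, and one added step in each exit script. No new visits or staff are needed. A single item does not give an MBP-MRAES score, and silent dropouts who answer no weekly survey stay unscored, which is why the never-assessed count should be shown.
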